# Title: Executive Functioning in TBI from Rehabilitation to Social Reintegration: COMPASS

## Grant: 1I01RX000637-01A3

### STUDY PROTOCOL

#### Study Summary

Traumatic brain injury (TBI) is a major health problem that leads to deficits in executive function, a term used for the cognitive operations responsible for planning, decision making, and other aspects of goal management. Executive functions are akin to the self-regulation processes by which humans manage their own thoughts, behaviors, and emotions in order to identify, prioritize, and meet goals. After TBI, which often affects the frontal regions of the brain and their connections, self-regulation processes become disordered and behavior may lose its goal-directed quality. This, along with other cognitive, physical, and behavioral deficits that follow TBI, contributes to injured Veterans' reduced ability to return to work or school and to regain satisfactory personal lives. Our understanding of the neurological disabling impact of TBI on executive function is necessary for both the accurate diagnosis of impairment and individual-tailoring of rehabilitation processes aimed at recovery of independent function in returning service members.

Goal-setting and goal management concepts are part of the "natural language" of rehabilitation. However, collaborative goal-setting between clinician/case manager and client can be difficult because of the cognitive deficits that follow TBI, and because clients with TBI have heterogeneous problems and diffuse goals that are difficult even for experienced clinicians to address. It might be argued that re-training returning Veterans with TBI how to self-manage their goals, with appropriate help and support, would essentially treat deficits in executive function. Such treatment would have multiple benefits: Practical, real-life goals would be achieved, and injured Veterans would re-learn the skills needed to manage their own goals in the future. A structured approach to goal self-management would foster greater independence and self-efficacy, help clients to gain insight into goals that are realistic for them at a given time, and help clinicians and clients to work more effectively as true collaborators.

The COMPASS (Community Participation through Self-Efficacy Skills Development) program aims at developing and testing a novel patient-centered intervention framework that can be utilized as a platform for VA community re-integration comparative effectiveness research. The COMPASSgoal intervention will be developed and implemented to meet these needs. COMPASSgoal will integrate principles and best practices of goal self-management. Goal setting is a core skill in self-management training by which persons with chronic health conditions learn to improve their status and decrease symptom impact. One important mechanism of action of this program appears to be its positive effect on self-efficacy, or confidence in one's ability to attain goals and solve problems.

The study goal is to gather data on the efficacy of a novel approach to psychosocial rehabilitation for Veterans with executive function impairment due to traumatic brain injury (TBI), and to explore over time, through relevant measures, Veteran responsiveness to intervention. Veterans with mild TBI will be randomized into two groups: the COMPASS (**Community** **P**articipation through **S**elf-Efficacy **S**kills Development) goal-management intervention group and the supported discharge group.

*110 participants with residual deficits in executive function due to TBI will be recruited at a minimum of 3 months post-injury from the TBI program at the DC VAMC over the three-year period of the study. The operational definition of executive dysfunction/ inclusion into the study is based on both clinical diagnosis by a study physician and a standardized executive dysfunction measure, the Frontal Systems Rating Scale (FrSBe score), such that a total score or any of the 3 subscale scores < 1 SD compared to the normative score would indicate executive dysfunction sufficient to include in the study. The treatment phase for the Veterans enrolled in the intervention group will continue for two consecutive months (8 weekly sessions). Each participant in the intervention and control group will be assessed at baseline (enrollment), post-intervention, and at 3 months post-treatment follow up.*

The COMPASS patient-centered intervention framework then can be utilized as a platform for VA community reintegration comparative effectiveness psychosocial research.

## SPECIFIC AIMS

The study main objective is to determine whether Operation Enduring Freedom/Operation Iraqi Freedom/Operation New Dawn (OEF/OIF/OND) Veterans with executive dysfunction due to traumatic brain injury (TBI) will benefit from a novel goal self-management intervention (Community Participation through Self-efficacy Skills Development, COMPASSgoal) compared to Veterans who receive case management support representing the current standard of care enhanced by an increased number of communication prompts as specified by the study protocol. 110 participants with residual deficits in executive function due to TBI will be recruited at least 3 months post-injury from the TBI program at the DC VAMC over the three year period of the study.

The specific aim and hypotheses of this project are:

Study Specific Aim 1: *To develop, implement, and evaluate a new goal self-management intervention (COMPASS) for Veterans with executive dysfunction due to mTBI, and to investigate how executive functioning is linked to the performance of everyday tasks and community functioning.*

### Study Hypotheses:

[figure not shown]
Study Hypothesis 1: Participants in the COMPASSgoal group will have higher TBI self-efficacy and higher community integration scores over time than participants in the supported discharge group matched on executive dysfunction score;

Study Hypothesis 2: *Individual psychosocial profile (emotional status, resilience, and level of post-traumatic stress disorder, PTSD) will mediate the responsiveness to the COMPASSgoal intervention, measured through the standardized experimental performance of everyday tasks, in Veterans with impaired executive function due to TBI.*

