### **Power and sample size calculation**

110 participants with executive dysfunction due to diagnosed TBI will be randomized into the COMPASSgoal intervention or supported discharge groups, as assessed via the VHA TBI Comprehensive Evaluation screening tool. Participants in the supported discharge group will not receive the intervention, but will receive usual care provided by case managers with increased intensity of communication prompts. Participants in the intervention group will receive 8 goal self-management sessions over a period of approximately 10 weeks. We don't expect a significant change from post-intervention to 3 month post-intervention, the sample size calculations are based on a t-test for comparisons of mean change in the Community Reintegration of Service members (CRIS) subscale from pre- to post-intervention between two groups.

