### **Hypothesis:**

H0:  $\mu_1 = \mu_2$  where  $\mu_1$ = mean change in CRIS subscale from time 1 to time 2 in self-management group and  $\mu_2$ = mean change in CRIS subscale from time 1 to time 2 in supported discharge group  
H1:  $\mu_1 \neq \mu_2$

**Power Calculation:** PASS (Power Analysis and Sample Size Software, Kaysville, UT, 2008) was used for the power calculation. The primary outcome of this study is the frequency of social interactions measured via the Extent of Participation subscale of the CRIS. The power calculation was performed based on the hypothesis listed above by using a two-sided t-test with assumption of normality. The level of significance was set at 0.05 and power was set at 90%. The effect size and standard deviation used for the power calculation were estimated based on a previous VA study and clinical judgment. 44 subjects in each

[figure not shown]
group, for a total of 88 subjects will provide 90% power to test an effect size of 0.71 with a SD of 7 for difference in CRIS subscale score between groups with  $\alpha=0.05$  (two sided). After adjustment for 20% loss to follow-up, we will recruit 55 subjects in each group of this study, a total of 110 subjects.

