## STATISTICAL ANALYSIS PLAN

### Overview

For this project, we plan to collect three major types of data assessed at times 1-3 (baseline/pre-intervention, 2 months/post-intervention, and 3 months follow up): community integration parameters including educational attainment and employment, individual characteristics such as PTSD; TBI self-efficacy, emotional status, coping, performance of real-world tasks, resilience and life satisfaction, and neuropsychological parameters including overall cognitive and executive functioning. Though we have removed the physical function assessments from future data collection, previously collected data on physical function may still be used for data analysis and subsequent publication and presentation purposes. The primary outcome will be the change in the three major types of parameters from pre- to post-intervention. Depending upon the hypothesis being tested (see Specific Aims section), participants will be stratified according to level of executive functioning, severity of conditions secondary to TBI (PTSD, level of functioning, emotional status), or degree of societal participation. Dependent variables will include TBI-self-efficacy, community integration indices, educational or work attainment as defined by the ICF qualifiers, and life satisfaction. Both objective (e.g. executive performance) and subjective (e.g., perceived TBI self-efficacy) data will then be obtained based on repeated measures over the three-year period. Multiple regression models will be fitted to explore continuous primary and secondary outcomes differentiating between groups at each time point and changes at the intra-individual and inter-individual levels over time. For categorical outcomes (e.g., low/high executive performance, or work status such as unemployed/employed, part-time/full-time), unconditional logistic and/or multinomial regression models will be implemented.

The basic testing of the hypotheses will involve ANOVA test and repeated measures ANOVA test. Bonferroni adjustments will be made to account for multiple testing.

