### **Hypothesis 1: Outcome Variables Main Effects for Community Re-integration Factors**

This algorithm is based on the assumption that an interaction between the intervention group and control groups can be modeled as a fixed effect. An LMM will then be used to evaluate whether the intervention had an effect at any time point or whether the intervention influenced change (growth, trajectory) in the outcome over the course of the study. The following will be considered for the analytical strategy:

- ANOVA, Repeated-measures ANOVA as well as MANCOVA will be used to compare the effect of the COMPASSgoal intervention vs. supported discharge group determined via baseline assessment. ANOVA will be used to compare the change from pre- to post-intervention between the two groups. Furthermore, in order to analyze the main effect of the COMPASSgoal intervention over time, a two-way repeated measures parametric ANOVA, as well as a non-parametric repeated measures Friedman ANOVA, will be performed, using the baseline time point, levels of TBI self-efficacy, or real-world tasks performance as the dependent variables. The levels of the repeated measures factor correspond to the number of assessments: baseline (pre-intervention) and 2 months post-intervention. The between-groups factor will be the intervention group vs. the supported discharge group. MANCOVA analysis will focus on the contrast in TBI self-efficacy between the intervention and supported discharge groups while accounting for a specified covariate: level of executive impairment as defined by FrSBE. In the case of non-normal residuals, we will use a nonparametric repeated measures approach. In the case of missing data, an LMM, which uses a maximum likelihood estimate to correct for unequal number of measures per subject, will be employed.
- *We will use Linear mixed models to control for potential confounding variables and baseline values will be utilized as a covariate. These models will allow for the additional control of potential within subjects clusters. These clusters, though not part of the formal hypothesis testing but byproducts of these models, will allow for conceptualization of additional future hypotheses.*

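### Hypothesis 1 claims gains in two outcomes, but the 90% power is for the CRIS test alone at 0.05, and no rule links that test to the Bonferroni adjustment or says how the two results decide the hypothesis

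*Combined protocol and SAP*

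**What the plan says.** - **The claim.** Under Study Hypotheses, Hypothesis 1 is that the COMPASS group "will have higher TBI self-efficacy and higher community integration scores over time than participants in the supported discharge group". The two outcomes are joined by a plain conjunction. The Overall Study Design section makes this the hypothesis that the randomised comparison tests.
- **The sized test.** Under Power and sample size calculation, the "sample size calculations are based on a t-test for comparisons of mean change in the Community Reintegration of Service members (CRIS) subscale", from before to after the intervention. The section that follows writes a formal null and alternative for that change only. It adds: "The primary outcome of this study is the frequency of social interactions measured via the Extent of Participation subscale of the CRIS". It also says "The level of significance was set at 0.05 and power was set at 90" percent, two-sided, and that 44 per "group, for a total of 88 subjects will provide 90% power to test an effect size of 0.71", with an SD of 7.
- **The multiplicity rule.** The SAP Overview says "Bonferroni adjustments will be made to account for multiple testing". It gives no family, number of tests or alpha per test. The same section describes the primary outcome differently: "The primary outcome will be the change in the three major types of parameters from pre- to post-intervention".
- **The Hypothesis 1 analysis.** In the SAP section for Hypothesis 1, the repeated-measures analysis names self-efficacy or real-world task performance as dependent variables, and "MANCOVA analysis will focus on the contrast in TBI self-efficacy between the intervention and supported discharge groups". The text under that heading does not name the CRIS.

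**The concern.** Three parts of the plan have to agree and do not. The claim covers two outcomes, the power covers one of them at the full 0.05, and the multiplicity rule would lower the alpha of any test it covers. The analyses named for Hypothesis 1 centre on the outcome that was not sized.

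The consequence shows in a split result. Suppose CRIS gives p = 0.03 and self-efficacy gives p = 0.20. Judged as the power section sets it up (CRIS at 0.05), the trial is positive. Under a two-test Bonferroni (0.025 each) or a rule requiring both outcomes, it is negative. Each of these fits some part of the text, so the reading of the main hypothesis could be settled after the results are known.

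**Working it through.** **Inputs from the documents.** 44 evaluable per arm, two-sided alpha 0.05, effect size 0.71, SD 7, 20% loss. The effect size must be read as standardised (0.71 × 7 = 4.97 points), since 0.71 points with an SD of 7 would give power of only about 0.08.

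**Inputs that are assumptions.** The documents give no self-efficacy effect and no correlation between the two outcomes. I use self-efficacy effects of 0.71 and 0.5, and correlations of 0 to 0.7.

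**1. The plan's own figure.** The noncentrality is d × √(n/2) = 0.71 × √22 = 3.330, with 86 degrees of freedom. At two-sided 0.05 the critical value is 1.988 and power is 0.909. Recruitment is 44 / 0.8 = 55 per arm, 110 in total. The stated sample size reproduces for CRIS alone at 0.05.

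**2. CRIS if Bonferroni covers it.** With two tests, alpha is 0.05 / 2 = 0.025, the critical value is 2.281 and power is 0.851. A larger family costs more: with three tests, alpha is 0.0167 and power is about 0.81.

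**3. Both results required.** The null hypothesis of the joint claim is that at least one outcome has no benefit. Declaring success only when both tests reject at 0.05 already holds the error of that claim at or below 0.05 (intersection-union test), so no split of alpha is needed. With independent outcomes, joint power is the product of the two powers:

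- 0.71 on both, 0.05 each: 0.909 × 0.909 = 0.83
- 0.71 on both, 0.025 each: 0.851 × 0.851 = 0.72
- self-efficacy 0.5 (noncentrality 0.5 × √22 = 2.345, power 0.640), 0.05 each: 0.909 × 0.640 = 0.58

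Simulated pairs of correlated t statistics extend these to correlation 0.7:

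| Rule | Self-efficacy effect | Power, correlation 0 to 0.7 |
|---|---|---|
| Both at 0.05 | 0.71 | 0.83 to 0.86 |
| Both at 0.025 | 0.71 | 0.72 to 0.78 |
| Both at 0.05 | 0.5 | 0.58 to 0.63 |

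**4. Either result suffices, with Bonferroni.** With independent outcomes and 0.71 on both, power for at least one success is 1 − (1 − 0.851)² = 0.98. It falls to 0.92 at correlation 0.7. This is above 90% throughout.

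**The case against.** The best defence is that CRIS is plainly the primary outcome. The power section says so and writes its formal hypotheses on it alone. The section on developing the intervention twice calls the CRIS the primary outcome measure. On that reading CRIS is tested at 0.05 with 90% power, self-efficacy is secondary, and no stated figure is wrong. Much of this stands: the 90% is attributed only to the CRIS difference, never to Hypothesis 1 as a whole. What it does not settle is whether the Bonferroni rule applies to the CRIS test, or what is concluded about a hypothesis that still names self-efficacy.

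Three stronger readings are tempting, and the documents do not support them.

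- **That power is below 90% however Hypothesis 1 is read.** It is not. Under an either-suffices rule with Bonferroni, power is 0.92 to 0.98 with 0.71 on both. Joint power also reaches about 0.90 if the self-efficacy effect is 0.9.
- **That the plan inflates the type I error.** Two uncorrected tests, with either one sufficing, would have an error rate of up to 1 − 0.95² = 0.0975. The SAP Overview commits to Bonferroni, so an uncorrected rule is not what is planned.
- **That Bonferroni is wrong.** If either result suffices, it is a proper correction. If both are required, it is valid but needlessly conservative, costing about 8 to 10 points of power in the table above.

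**Conclusion.** The concern holds as a mismatch that is cheap to repair. The plan does not establish 90% power for the two-part claim in Hypothesis 1, and it leaves open how a split result is judged. The CRIS figure of 90% is sound for that test at 0.05. It becomes about 0.85 if the SAP's own Bonferroni rule covers the two outcomes, and lower for a larger family. The drop to 0.85 uses only the plan's figures and a family of two.

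The joint-power figures depend on assumptions that the documents do not supply: about 0.58 to 0.86 at 0.05 each, for self-efficacy effects of 0.5 to 0.71 and correlations of 0 to 0.7. The missing decision rule does not depend on any of them.

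**What to change.** In the SAP Overview and the Hypothesis 1 section, state one rule:

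1. Test the change in CRIS Extent of Participation from baseline to post-intervention first, at two-sided 0.05.
2. Test TBI self-efficacy at two-sided 0.05 only if the CRIS test is significant.
3. Apply no Bonferroni adjustment between these two. Limit it to the remaining outcomes and list them.
4. Declare Hypothesis 1 as worded supported only if both results favour COMPASS. If only CRIS is significant, claim community integration only.

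In the power section, say that 90% is the power of the CRIS test at 0.05 and nothing more. If joint power is reported, give it as a range over the assumed self-efficacy effect and correlation (for example 0.58 to 0.86 for effects of 0.5 to 0.71), not as 0.83 to 0.86 alone.

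This keeps the sized test at the alpha it was sized on, controls the error rate across the two outcomes and fixes the reading of a split result. Other rules would also be coherent, such as both required or either with a stated split. The fixed sequence is the one that leaves the existing CRIS calculation intact. The change is to wording only, with no extra participants or data. The cost is that self-efficacy becomes exploratory if CRIS is not significant.

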### ***Overall Study Population***

*One hundred and ten Veterans with residual deficits in executive function due to mild TBI will be recruited from the TBI clinics at the DC VAMC over the three-year period of the study. Severity of TBI will be determined by the DC VAMC attending clinician using the VHA TBI Comprehensive Evaluation electronic template. The Frontal Systems Rating Scale (FrSBe) will be used to identify individuals with differing levels of executive dysfunction. The operational definition of executive dysfunction/ inclusion into the study is based on both clinical diagnosis by a study physician and a standardized executive dysfunction measure, the FrSBe score, such that a total score or any of the 3 subscale scores < 1 SD compared to the normative score would indicate executive dysfunction sufficient to include in the study.* Prior history of known bipolar disorder, schizophrenia or severe psychiatric illness will be determined first by review of the medical history. If the potential participant's medical record has no documentation of mental health evaluation within the year prior to enrollment, the M.I.N.I. Neuropsychiatric Interview will be administered for exclusionary screening purposes..

We will make every effort to balance the sample by age, gender, and education following the study inclusion-exclusion criteria. Based on previous studies conducted with the VA population in the Greater Washington Area, we expect that approximately 10% of the study participants will be female, and 70% will be African-American. The total number of study participants (N = 110) accounts for a 20% attrition rate in a neurologically-disabled population due to their health condition and related problems.

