## RANDOMIZATION OF THE COMPASS PARTICIPANTS

Randomization of the study participants will occur after all the baseline data are collected. The mTBI diagnosis including operational definition of executive dysfunction will be determined by the study Co-PI, [name], Director of the TBI Program at the DC VAMC with the participation of the DC VAMC neuropsychologist as part of the routine evaluation of Veterans referred with suspected TBI. Staff performing all outcome assessments will be blinded to group assignment throughout the study, and participants will be asked at each assessment not to reveal their group assignment to data collectors.

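### Hypothesis 1 promises a control group matched on executive dysfunction; no described step matches on it, and the FrSBe is not named in the analysis of the primary CRIS outcome

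*Combined protocol and SAP*

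**What the plan says.** - **Study Hypotheses.** Under Hypothesis 1 the comparator is "participants in the supported discharge group matched on executive dysfunction score". The outcomes are TBI self-efficacy and community integration.
- **Randomization of the COMPASS Participants.** On allocation, the section gives timing: "Randomization of the study participants will occur after all the baseline data are collected". It otherwise covers who confirms the diagnosis and the blinding of assessors. It names no allocation method, matching or stratification factor.
- **Overall Study Population.** The only balancing statement is "We will make every effort to balance the sample by age, gender, and education". Executive function is not in that list, and no mechanism is given.
- **SAP, Overview.** Depending on the hypothesis, "participants will be stratified according to level of executive functioning", or by severity of secondary conditions, or by degree of societal participation. It does not say which option serves Hypothesis 1, whether this happens at randomization or in the analysis, or where the cut-points lie.
- **SAP, Hypothesis 1.** "MANCOVA analysis will focus on the contrast in TBI self-efficacy between the intervention and supported discharge groups", "accounting for a specified covariate: level of executive impairment as defined by FrSBE". The ANOVA of pre-post change names no covariate. The mixed model adjusts for baseline values and for confounders that are not listed.
- **Power and sample size calculation.** The primary outcome is the CRIS Extent of Participation subscale, and the sample size rests on an unadjusted two-sided t-test of change: "we will recruit 55 subjects in each group of this study, a total of 110 subjects".

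**The concern.** Matching is a property of the design. A reader of Hypothesis 1 would expect the arms to be aligned on executive dysfunction by construction, yet the text describes nothing that would align them. If adjustment is meant to do this work instead, it is specified for self-efficacy and not for the CRIS, the outcome on which the trial is sized. Leaving the mixed model's confounders unnamed also lets the choice of covariates be made after the data are seen.

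At stake are precision and the credibility of the primary comparison. Executive dysfunction defines the population, and the score is in hand before allocation, so leaving it out of the primary model gives up whatever precision it offers.

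**Working it through.** **1. The plan's own sample size.** Inputs from the power section: effect size 0.71, SD 7, two-sided alpha 0.05, power 90%, 20% loss.

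- Normal approximation: n = 2(1.960 + 1.282)² / 0.71² = 41.7, so 42 per group. The t-test version gives 42.7, so 43. The plan states 44.
- Power at 44 per group by t-test: 0.909.
- Loss to follow-up: 44 / (1 − 0.20) = 55 per group, 110 in total.

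The figure reproduces if 0.71 is a standardized effect, that is 0.71 × 7 = 4.97, about 5 CRIS points. Read as 0.71 raw points on an SD of 7, it would need 2043 per group.

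**2. Chance imbalance in the FrSBe.** This assumes unstratified 1:1 allocation. The documents state no method; equal arms follow from 55 per group. The difference in arm means, in FrSBe SD units, has standard error √(2/n).

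| n per arm | SE | 95% range | P(difference beyond 0.25 SD) |
|---|---|---|---|
| 55 | 0.191 | ±0.37 | 0.19 |
| 44 | 0.213 | ±0.42 | 0.24 |

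**3. Effect on the CRIS comparison.** The documents give no correlation r between baseline FrSBe and CRIS change, so r is an assumption shown over a range.

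- Shift in the unadjusted difference for a 0.25 SD imbalance: r × 0.25 × 7.
- Shift at the 95% limit with 44 per arm: r × 0.418 × 7.
- Residual variance after adjustment: 1 − r². Effective standardized effect: 0.71 / √(1 − r²).

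| Assumed r | Shift at 0.25 SD (points) | Shift at 95% limit (points) | Residual variance | Effective d | Power at 44 per arm |
|---|---|---|---|---|---|
| none (unadjusted) | – | – | 1.00 | 0.710 | 0.909 |
| 0.1 | 0.18 | 0.29 | 0.99 | 0.714 | 0.911 |
| 0.3 | 0.53 | 0.88 | 0.91 | 0.744 | 0.932 |
| 0.5 | 0.88 | 1.46 | 0.75 | 0.820 | 0.967 |

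Against a planned difference of 4.97 points, a 0.25 SD imbalance is worth 0.18/4.97 = 4% at r = 0.1, 0.53/4.97 = 11% at r = 0.3 and 0.88/4.97 = 18% at r = 0.5.

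**4. Is the covariate available in time?** The Sampling section says everyone who consents is examined with the FrSBe, and randomization follows completion of baseline data. It is therefore known before allocation.

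**The case against.** The strongest reply is that the documents leave routes by which executive function could enter the CRIS analysis. The Overview speaks of stratifying by it, and the mixed model's unnamed confounders could include it. The same model already plans baseline values as covariates, so baseline CRIS is arguably covered. The study algorithm figure is not available here and may carry allocation detail. This stands as far as it goes. A reader might infer that balance on executive dysfunction is impossible or ruled out for the CRIS; the documents do not support that. They show a promise left unspecified and sections that disagree. The Overview's stratification varies with the hypothesis and lists alternatives, whereas a trial is randomized once, so it does not read as an allocation scheme.

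A second tempting inference is that missing matching biases the treatment comparison. It does not: randomization balances the score in expectation, and chance imbalance leaves the test valid.

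Third, the gain may be small. In describing the recruitment assessment, the protocol cites a prior study in which the FrSBe predicted community integration only weakly, although it used a different integration measure that the protocol itself criticizes. Selecting participants for executive dysfunction may weaken the correlation further, and FrSBe may add less once baseline CRIS is in the model. Unadjusted power already exceeds 90%. All of this stands and limits the size of the point.

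**Conclusion.** The point holds as an inconsistency with a modest cost in precision. Hypothesis 1 claims a matched comparison that the described design does not have, and the FrSBe is specified as a covariate for self-efficacy but not for the CRIS. The textual mismatch does not depend on any correlation. The statistical gain does: power at 44 per arm rises by 0.002 at r = 0.1, 0.023 at r = 0.3 and 0.058 at r = 0.5, with FrSBe as the only covariate. These figures assume unstratified 1:1 allocation and the standardized reading of 0.71. They treat the CRIS subscale as primary, as in the power section; the SAP Overview words the primary outcome more broadly.

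**What to change.** 1. **SAP, Hypothesis 1.** Replace the unadjusted ANOVA of change, as the primary CRIS comparison, with a model adjusted for continuous baseline FrSBe and baseline CRIS. Name the FrSBe score to be used, since the scale yields a total and three subscales. In the self-efficacy MANCOVA, state that the FrSBe covariate is the baseline value; executive functioning is assessed at all three times and the text does not say which is meant.
2. **Study Hypotheses.** In Hypothesis 1, replace *matched on* with *adjusted for baseline*.
3. **SAP, Overview.** State whether stratification by executive functioning applies to Hypothesis 1, and whether it is done at randomization or in the analysis.

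Stratifying the randomization by FrSBe is optional. Once the covariate is in the primary model, the case for it in a single-site trial of 110 is debatable.

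The cost is one further covariate, already collected before randomization. The sample size does not change.
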